15.3 Clinical Laboratory Evaluation

Listings and summary statistics at each assessment time will be presented using SI units. Normal ranges will be provided by the laboratory department, and out of range flags will be calculated based on the normal ranges. Laboratory data not transferred from the central laboratory in SI units will be converted to SI units before processing. Both original units and SI units will be provided in the SDTM domain.

Safety laboratory parameters are separated into:

- Hematology (including coagulation)
- Biochemistry
- Urinalysis
- Other tests

Hematology, biochemistry, and coagulation will be summarized overall by time point using descriptive statistics for baseline (see definition in Section 9), each evaluation during the study, and change from baseline to each evaluation.

Listings of abnormal test results (low and high) will also be provided.

15.4 Vital Signs

Vital signs data will be summarized overall by time point using descriptive statistics for baseline (see definition in Section 9), each evaluation during the study, and change from baseline to each evaluation. Listings of vital sign data will be provided.

Vital sign summaries will include all vital sign assessments from the on-treatment period. All vital sign assessments will be listed, and those collected outside the on-treatment period will be flagged in the listing.

15.5 Other Safety or Tolerability Evaluations

Safety ECG data will be summarized overall by time point using descriptive statistics for baseline (see definition in Section 9), each evaluation during the study, and change from baseline to each evaluation. A listing of safety ECG data will be provided.

ECG summaries will include all ECG assessments from the on-treatment period. All ECG assessments will be listed.

The analysis of QT data is complicated by the fact that the QT interval is highly correlated with heart rate. Because of this correlation, formulas are routinely used to obtain a corrected value, denoted QTc, which is independent of heart rate. This QTc interval is intended to represent the QT interval at a standardized heart rate. The QT interval will be corrected for heart rate by the Fridericia's formula, QTcF, defined as

$$QTcF = \frac{QT}{\sqrt[3]{RR}} ,$$

where RR represents the RR interval of the ECG in seconds, and can be estimated as 60/Heart Rate.

Investigator-reported interpretation results will also be tabulated by study intervention and time point using the number and percentage of participants for each interpretation category (Normal, Abnormal Not Clinically Significant [NCS], Abnormal Clinically Significant [CS]).

16 Analyses of Other Endpoints/Estimands

16.1 Pharmacokinetics

PK evaluation will be performed by Nuvisan GmbH.

All statistical analyses and descriptive summaries of PK data will be performed on the PK Analysis Set.

16.1.1 Descriptive Statistics of PK Concentration Data

PK measurements of evobrutinib and its metabolite MSC2729909A [REDACTED] CCI [REDACTED] will be descriptively summarized using: number of non-missing observations (n), arithmetic mean (Mean), SD, coefficient of variation (CV%), minimum (Min), median (Median) and maximum (Max).

Descriptive statistics will only be calculated for n > 2 in which a measurement of BLQ represents a valid measurement and will be taken as zero for summary statistics of PK concentration data.

Any mean or median value that is below the lower limit of quantification will be shown as BLQ.

Descriptive statistics of PK concentration data will be calculated using values with the same precision as the source data and rounded for reporting purposes only. In export datasets, as well as in the SDTM PC domain, PK concentrations will be provided with full precision and will not be rounded.

The following conventions will be applied when reporting descriptive statistics of PK concentration data:

n 0 decimal place

Mean, Min, Median, Max: 3 significant digits

SD: 4 significant digits

CV%: 1 decimal place

16.1.2 Descriptive Statistics of PK Parameter Data

PK parameter data of evobrutinib and its metabolite MSC2729909A on Day 1 and Day 19 as well

CCI [REDACTED] Day 19 of using: number of non-missing observations (n), arithmetic mean (Mean), SD, coefficient of variation (CV%), minimum (Min), median (Median), maximum (Max), geometric mean (GeoMean), the geometric coefficient of variation (GeoCV) and the 95% confidence interval for the GeoMean (LCI 95% GM, UCI 95% GM). For PK parameters related to time (e.g. t_{max} , t_{lag} , t_{last}), only n, Min, Median, and Max may be reported.

Descriptive statistics will only be calculated for a PK parameter when $n > 2$.

PK parameters read directly from the measurements (i.e., C_{max}) will be reported with the same precision as the source data. All other PK parameters will be reported to 3 significant figures. In export datasets, as well as in the SDTM PP domain, PK parameters will be provided with full precision and will not be rounded. Descriptive statistics of PK parameter data will be calculated using full precision values and rounded for reporting purposes only.

The following conventions will be applied when reporting descriptive statistics of PK parameter data:

n 0 decimal place

Mean, Min, Median, Max, GeoMean, 95% CI: 3 significant digits

SD: 4 significant digits

CV%, GeoCV%: 1 decimal place

16.1.3 Statistical Analysis of PK Parameter Data

Analysis of Primary Endpoints

The effect of co-administration of carbamazepine on evobrutinib exposure will be assessed. A general linear model with a fixed effect for TREATMENT and a random effect for SUBJECT will be applied to the log-transformed PK parameters C_{max} and $AUC_{0-\infty}$ based on the PK analysis set.

Treatment differences on the log scale of evobrutinib with carbamazepine versus evobrutinib alone (Day 19 versus Day 1) will be estimated for the C_{max} and $AUC_{0-\infty}$ together with their 90% CIs. Point estimates and CIs will be back transformed to the original scale for presentation.

Analysis of Secondary Endpoints

The same analysis model as described for the primary endpoints will be provided for the secondary endpoint AUC_{0-tlast} of evobrutinib and C_{max}, AUC_{0-tlast} and AUC_{0-∞} of the evobrutinib metabolite MSC2729909A in plasma.

CCI

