9.4.3 Pharmacokinetic Analyses

Details on the PK analysis will be in the IAP that will be finalized before database lock.

Reference #	Endpoint	Statistical Analysis
Primary		
1 – Evobrutinib PK	AUC _{0-∞} and C _{max}	The effect of co-administration of carbamazepine on evobrutinib exposure will be assessed. A general linear model with a fixed effect for TREATMENT and a random effect for SUBJECT will be applied to the log-transformed PK parameters C _{max} and AUC _{0-∞} based on the PK analysis set. Treatment differences on the log scale of evobrutinib with carbamazepine versus evobrutinib alone (Day 19 versus Day 1) will be estimated for the C _{max} and AUC _{0-∞} together with their 90% CIs. Point estimates and CIs will be back transformed to the original scale for presentation. Summary statistics will be provided for AUC _{0-∞} and C _{max} .
Secondary		
3 – Additional evobrutinib PK parameters	CL/F, Vz/F, AUC _{0-tlast} , t _{max} , t _{1/2}	The same analysis model as described for the primary endpoints will be provided for the secondary endpoint AUC _{0-tlast} of evobrutinib in plasma. Summary statistics will be provided for all PK parameters.

4 – Evobrutinib metabolite (MSC2729909A) PK	AUC _{0-∞} , AUC _{0-t_{last}} , C _{max} , t _{max} t _{lag} and the respective metabolic ratios MR(AUC _{0-∞}) and MR(C _{max})	The same analysis model as described for the primary endpoints will be provided for the secondary endpoints C _{max} , AUC _{0-t_{last}} and AUC _{0-∞} of the evobrutinib metabolite MSC2729909A in plasma. Summary statistics will be provided for all PK parameters.
CCI		
CCI		

AUC=area under the concentration-time curve; C_{max}=maximum observed concentration; C_{min}=minimum observed concentration; CL/F=apparent total body clearance; MR=metabolic ratio; PK=pharmacokinetics; t_½=apparent terminal half-life; t_{lag}=time prior to the first measurable (nonzero) concentration; t_{max}=time to reach the maximum observed concentration; Vz/F=apparent volume of distribution.

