To assess the safety and tolerability of evobrutinib when administered together with carbamazepine in healthy participants	
 Nature, occurrence, severity, and seriousness of TEAEs Absolute values and changes in safety laboratory tests from time of first dose to end of study participation Single 12-lead ECGs evaluated by Investigator from time of first dose to end of study participation Vital signs assessed from time of first dose to end of study participation 	2
To characterize the effect of carbamazepine on additional evobrutinib PK parameters in healthy participants	
 Plasma evobrutinib: CL/F Plasma evobrutinib: V_z/F Plasma evobrutinib: $AUC_{0-t_{last}}$ Plasma evobrutinib: t_{max} Plasma evobrutinib: $t_{1/2}$ 	3
To characterize the effect of carbamazepine on evobrutinib metabolite (MSC2729909A) PK in healthy participants	
 Plasma MSC2729909A: $AUC_{0-\infty}$ Plasma MSC2729909A: $AUC_{0-t_{last}}$ Plasma MSC2729909A: C_{max} Plasma MSC2729909A: t_{max} Plasma MSC2729909A: $t_{1/2}$ Plasma MSC2729909A: metabolite to parent ratios $M/P(AUC_{0-\infty})$ and $M/P(C_{max})$ 	4
CCI		
	  	
	  	
	  	

AUC=area under the concentration-time curve; C_{max} =maximum observed concentration; C_{min} = minimum observed concentration; CL/F =apparent total body clearance; ECG=electrocardiogram; M=metabolite; P=parent; PK=pharmacokinetics; TEAE=treatment emergent adverse event; $t_{1/2}$ =apparent terminal half-life; t_{lag} =time prior to the first measurable (nonzero) concentration; t_{max} =time to reach the maximum observed concentration; V_z/F =apparent volume of distribution.

6 Overview of Planned Analyses

The final, planned analyses identified in the CSP and in this IAP will be performed after the last participant has completed the last visit and after all data queries resolved as well as the database locked.

A data review meeting will be held prior to database lock for the final analysis. In addition, no database can be locked until this IAP has been approved.

7 Changes to the Planned Analyses in the Clinical Study Protocol

An interim data review may occur if necessary for data evaluation in order to make decision on the dosing of subjects. In that case, an unplanned interim analysis request form will be submitted for approval to the Head of GBS and the decision will be thoroughly documented.

8 Analysis Sets and Subgroups

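### The effect of carbamazepine on metabolite-to-parent ratios and half-life is a stated objective, but no Day 19/Day 1 estimate or interval is prespecified for them

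*SAP*

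**What the plan says.** SAP Section 5 words two secondary objectives as effects. Objective 3 reads "To characterize the effect of carbamazepine on additional evobrutinib PK parameters in healthy participants" and lists evobrutinib t1/2 among its endpoints. Objective 4 reads "To characterize the effect of carbamazepine on evobrutinib metabolite (MSC2729909A) PK in healthy participants" and includes the "metabolite to parent ratios" for AUC0-inf and Cmax. The SAP and the protocol synopsis also list metabolite t1/2 under objective 4.

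For the primary endpoints, SAP 16.1.3 specifies the model: "A general linear model with a fixed effect for TREATMENT and a random effect for SUBJECT will be applied to the log-transformed PK parameters", here Cmax and AUC0-inf of evobrutinib. Day 19 is compared with Day 1 and the differences are reported "together with their 90% CIs". The section then turns to the secondary endpoints: "The same analysis model as described for the primary endpoints will be provided for the secondary endpoint". It names four: evobrutinib AUC0-tlast, and metabolite Cmax, AUC0-tlast and AUC0-inf. A redacted block follows.

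Protocol 9.4.3 names the same four and covers the rest with "Summary statistics will be provided for all PK parameters".

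SAP 16.1.2 describes those summaries, which include a 95% CI for the geometric mean. It also allows time-related parameters to be reported with n, minimum, median and maximum only. SAP 16.1.6.1 tabulates parameters by study intervention. In SAP 16.1.6.2 the spaghetti plot covers primary parameters only, and the boxplots omit M/P and t1/2.

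**The concern.** The study is single-sequence and each participant is measured on both days, so the natural estimate of an effect is the within-participant Day 19/Day 1 ratio. The plan uses it for six exposure parameters and not for M/P or t1/2, although their objectives use the same effect wording.

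A reader of the study report would have two separate summaries, one per day, for these endpoints. A confidence interval for each day's geometric mean is not an interval for the change between days, and setting two of them side by side discards the pairing. For t1/2 even the two geometric means might be absent. What is at stake is how precisely, and how visibly as a prespecified result, two named secondary questions are answered.

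**Working it through.** The documents give no figure to reproduce here. The trial's variability table and the precision table by within-subject CV are redacted, so all CVs below are assumptions.

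**1. Endpoints against planned analyses**

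| Endpoint | Paired model with 90% CI | Otherwise |
|---|---|---|
| Evobrutinib Cmax, AUC0-inf, AUC0-tlast | yes | |
| Metabolite Cmax, AUC0-inf, AUC0-tlast | yes | |
| M/P(AUC0-inf), M/P(Cmax) | no | summary per study intervention |
| t1/2 | no | summary per study intervention, possibly n, min, median, max only |
| Vz/F, tmax | no | summary per study intervention |
| CL/F | no | at fixed dose its ratio and CI are the reciprocals of those for AUC0-inf |

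**2. What can be rebuilt for M/P from planned tables**

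- Point estimate. On the log scale, change in M/P = change in metabolite minus change in parent. So GMR(M/P) = GMR(metabolite) / GMR(parent), and the molecular-weight factor cancels. In a simulated data set with 18 complete pairs, the direct paired estimate, the quotient of the two GMRs (0.7495 / 0.3508) and the quotient of the per-day geometric means all gave 2.137.
- Condition. The identity is exact only on the same complete pairs. The PK analysis set (SAP 8.1) requires nonmissing primary endpoints, which are parent parameters. A participant lacking metabolite AUC0-inf would still count in the parent ratio.
- Interval. Var(M/P) = Var(metabolite) + Var(parent) - 2 Cov. No planned model or summary table reports the covariance. Take n = 18, t(0.95, 17) = 1.740, both within-subject CVs 20%, s = sqrt(ln(1 + 0.20^2)) = 0.198, and the SE of each log ratio = 0.198 x sqrt(2/18) = 0.0660. The 90% factor is then exp(1.740 x 0.0660 x sqrt(2(1 - r))):
  - r = -0.5: 1.22
  - r = 0: 1.18
  - r = 0.9: 1.05
- At CV 30% the factor runs from 1.27 (r = 0) to 1.08 (r = 0.9).

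**3. Cost of comparing the days without pairing**

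Log half-widths with n = 18 and s = sqrt(ln(1 + CV^2)):

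- paired: t(0.95, 17) x s_w x sqrt(2/18)
- unpaired: t(0.95, 34) x sqrt(s_b^2 + s_w^2) x sqrt(2/18)

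Example with between-subject CV 30% and within-subject CV 15% (s_b = 0.2936, s_w = 0.1492): paired 1.740 x 0.1492 x 0.3333 = 0.0865; unpaired 1.691 x 0.3293 x 0.3333 = 0.186; quotient 2.15.

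| Between-subject CV | Within 15% | Within 25% |
|---|---|---|
| 10% | 1.17 | 1.05 |
| 15% | 1.37 | 1.14 |
| 30% | 2.15 | 1.51 |
| 50% | 3.23 | 2.10 |

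For t1/2 the upper rows may be closer. Protocol 2.2 gives a median of about 2 hours with a range of 1.8 to 2.6 hours, but does not say whether that range is over individuals or over dose groups.

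**4. What the planned model would give**

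With n = 18, the 90% CI is the GMR multiplied by these limits, according to the endpoint's own within-subject CV: 0.944 to 1.060 (10%), 0.892 to 1.122 (20%), 0.843 to 1.186 (30%), 0.800 to 1.250 (40%).

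**The case against.** The strongest reply is that the choice is consistent and declared. Protocol 9.1 says the analysis is descriptive without hypothesis tests. Protocol 9.4.3 and SAP 16.1.3 give the same list of modelled parameters, and the objectives only promise to characterize. All of this is correct, and the two documents do not conflict. But ruling out tests does not rule out estimation: the same plan gives 90% CIs for six parameters, and the request is for estimates on that footing.

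A reader might infer that the paired effect on M/P or t1/2 is lost. The documents do not support that. SAP 16.1.6.1 plans listings of individual parameters by participant and day, from which an exact paired interval could be computed. Under SAP Section 4, though, such an analysis would have to be identified in the study report as post hoc or unplanned.

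A reader might also take a two- or threefold loss of precision as established. It is not. It rests on assumed between-subject CVs of 30% to 50% and on an unpaired comparison that neither document plans.

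Finally, the redacted block after the secondary-endpoint text could in principle contain more. The matching visible lists in both documents make a hidden model for M/P or t1/2 unlikely, but this cannot be checked.

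**Conclusion.** The point holds as a low-severity gap between objectives and analysis. In the visible text, no Day 19/Day 1 effect or interval is prespecified for M/P(AUC0-inf), M/P(Cmax) or t1/2. The M/P point effect follows from the modelled ratios on common complete pairs; its interval needs an unplanned analysis of the listings. For t1/2, SAP 16.1.2 leaves open whether per-day geometric means will be shown at all: its time-parameter rule gives tmax, tlag and tlast as examples and does not mention t1/2.

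The loss from ignoring the pairing ranges from about 1.05 to 3.2 times in log width over the assumed CVs and cannot be narrowed from the public text. The gap itself does not depend on those CVs. The primary endpoints and the modelled exposure parameters of both analytes are unaffected.

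**What to change.** In SAP 16.1.3, extend the secondary-endpoint sentence so that the same log-scale model is also applied to M/P(AUC0-inf), M/P(Cmax) and t1/2 of evobrutinib, and to t1/2 of the metabolite where estimable. Report Day 19/Day 1 geometric mean ratios with 90% CIs, labelled as descriptive estimates without tests. Vz/F, a named endpoint under the same objective as evobrutinib t1/2, can be added in the same way. CL/F needs no separate model.

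The cost is an SAP wording change, a few more runs of a model already planned, and some extra table rows. Sample size and data collection do not change.

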16.1.4 General Specifications for PK Concentration and PK Parameter Data

Predose samples that occur before the first drug administration will be assigned a time of 0 hours, as if the sample had been taken simultaneously with the study intervention administration. Same applies to the pre-dose sample after multiple doses.

Predose or trough samples which have been taken after the subsequent dosing will be reported as a protocol deviation. The resulting concentrations will be included in concentration listings but excluded from descriptive statistics of concentrations and from PK parameter estimation.

Values BLQ will be taken as zero for summary statistics of PK concentration data, PK parameter estimation (e.g., AUC) and for graphical presentations.

Missing concentrations (e.g., no sample, insufficient sample volume for analysis, no result or result not valid) will be reported generally as “N.R.”. A participant who withdraws prior to the last planned observation will be included in the analyses up to the time of discontinuation if still included in the PK analysis set.

If samples are collected outside of 10% of the PK sampling time windows defined in the CSP in Section 8.4, these will be included in the PK parameter estimation (NCA) but will be excluded from the concentration summary and mean/median concentration plots.

PK concentrations which are erroneous due to a sampling processing or analytical error (as documented in the bioanalytical report) may be excluded from the PK analysis if agreed by the Sponsor. In this case the rationale for exclusion will be provided in the CSR. Any other PK concentrations that appear implausible to the Clinical Pharmacologist/Clinical PK/PD Scientist will not be excluded from the analysis. Any implausible data will be documented in the CSR.

If important protocol deviations occurred likely to affect the PK profile of participants as specified in Section 10.2.1, the impacted concentrations and PK parameters will be excluded from summary statistics and further statistical evaluation.

Any PK concentrations or PK parameters excluded from summary statistics will be included in participants listings and flagged; a reason for exclusion will be detailed in the CSR (e.g., a footnote or a table of exclusions). Any flags will be included in the study specific CDISC data sets.

PK concentrations and PK parameters excluded from summary statistics will not be included in mean/median figures. Mean plots will only contain values where $n > 2$.

16.1.5 Estimation of Pharmacokinetic Parameters

The computer program Phoenix® WinNonlin® version 6.4, or higher (Certara, L.P., [name]) will be used to derive PK parameters applying NCA.

The statistical software SAS® (Statistical Analysis System, SAS-Institute, Cary NC, USA, windows version 9.1 or higher) will be used to generate additional PK parameters and produce tables, listings, and figures.

16.1.5.1 Estimation of Pharmacokinetic Parameters in Plasma

PK parameters will be calculated using the actual elapsed time since dosing. If the actual sampling time is missing, calculations may be performed using the scheduled time. Details (e.g., number of samples, participants affected) will be described in the CSR. If actual dosing time is missing, scheduled time might be used for NCA after performance of adequate plausibility checks and agreement with the sponsor. Decision and rational should be included in the CSR. Otherwise, there will be no further imputation of missing data.

The following plasma PK parameters will be calculated, when appropriate, for evobrutinib and its metabolite MSC2729909A on Day 1 and Day 19:

Symbol	Definition
$AUC_{0-\infty}$	The AUC from time zero (= dosing time) up to infinity with extrapolation of the terminal phase.
$AUC_{0-t_{last}}$	The AUC from time zero (= dosing time) to the time of the last quantifiable concentration (t_{last}).
C_{max}	Maximum observed concentration.
t_{max}	The time to reach the C_{max} in a dosing interval.
$t_{1/2}$	The terminal half-life.
t_{lag}	The time prior to the first concentration at or above LOQ
CL/F	The apparent total body clearance following extravascular administration.
V_z/F	The apparent volume of distribution during the terminal phase following extravascular administration.
$M/P(AUC_{0-\infty})$	Molecular weight-corrected ratio of metabolite $AUC_{0-\infty}$ to parent $AUC_{0-\infty}$. $M/P(AUC_{0-\infty}) = AUC_{0-\infty} \text{ metabolite} \times \text{MW parent} / (AUC_{0-\infty} \text{ parent} \times \text{MW metabolite})$
$M/P(C_{max})$	Molecular weight-corrected ratio of metabolite C_{max} to parent C_{max} . $M/P(C_{max}) = C_{max} \text{ metabolite} \times \text{MW parent} / (C_{max} \text{ parent} \times \text{MW metabolite})$

MW of evobrutinib is 429.52 g/mol. MW of its metabolite MSC2729909A is 463.5289 g/mol.

CCI

CCI	

Units for PK parameter outputs will be based on concentration and dose units used in the study, unless otherwise specified. If concentration data units change within the study, PK parameters will be reported using consistent units throughout study outputs. In such cases, the Sponsor will specify relevant units for reporting before the final PK evaluation.

The parameters C_{max} and t_{max} will be obtained directly from the concentration-time profiles. If C_{max} occurs at more than one timepoint, t_{max} will be assigned to the first occurrence of C_{max} .

The following PK parameters will be calculated for diagnostic purposes and listed, but will not be summarized:

- First (λ_z low) and last (λ_z up) time point of the time interval of the log-linear regression to determine λ_z .
- Number of data points ($N\lambda$) included in the log-linear regression analysis to determine λ_z .
- Goodness of fit statistic (adjusted R^2) for calculation of λ_z .
- AUC from time t_{last} extrapolated to infinity given as percentage of $AUC_{0-\infty}$. ($AUC_{extra\%}$)
- Span ratio of interval over which $t_{1/2}$ was estimated/ $t_{1/2}$

The regression analysis should contain data from at least 3 different time points in the terminal phase consistent with the assessment of a straight line on the log-transformed scale. Phoenix WinNonlin “best fit” methodology will be used as standard. If warranted, further adjustment may be made by the pharmacokineticist, after agreement with the Sponsor. The last quantifiable concentration $> LLOQ$ should always be included in the regression analysis, while the concentration at t_{max} and any concentrations BLQ which occur after the last quantifiable data point $> LLOQ$ should not be used.

If $AUC_{extra\%} > 20\%$ and/or the coefficient of correlation (R^2 adj) of λ_z is < 0.8 and/or the observation period over which the regression line is estimated (span ratio) is less than 2-fold the resulting $t_{1/2}$, the rate constants and all derived parameters (e.g. $t_{1/2}$, $AUC_{0-\infty}$, CL/F , etc.) will be listed, flagged and included in the parameter outputs. Should more than 10% of subjects be flagged for AUC_{extra} and/or R^2 adj (for a particular analyte), a sensitivity analysis excluding flagged parameters may be performed after discussion with the Sponsor.

